#### 4.2.2 Per-protocol (PP)

The per-protocol analysis set will be limited to patients who actually received the exam to which they were randomly assigned and who have no major protocol violations.

#### 4.2.3 Safety population

The safety analysis set includes all participants who underwent at least one of the imaging diagnostic procedures under investigation, regardless of protocol adherence. This set will be used for all safety-related analyses, including the assessment of adverse events potentially related to the imaging procedures, any procedural complications, and other safety parameters collected during the study. Participants will be analysed according to the imaging method actually received. No exclusions will be made based on deviations from the protocol or missing data for the safety analysis.

This approach ensures that all safety information associated with the diagnostic procedures is comprehensively captured, independent of the primary efficacy analysis, which focuses on diagnostic accuracy.

## 5. Protocol compliance and deviations

Protocol deviations will be identified prospectively and retrospectively.

**Major protocol deviations** are deviations that may affect the integrity of the trial, compromise the evaluation of the primary outcome, or threaten the validity of the randomization. The following cases are predefined as major protocol deviations:

- The blinding of the radiological examinations to be masked from the treating physicians was broken before or during the clinician assessment of the probability of pneumonia

No **minor protocol deviations** have been predefined in the protocol. However, any deviations not meeting the definition of a major deviation will be reviewed and, if applicable, **summarized descriptively** (number and frequency) for reporting purposes.

All protocol deviations will be documented and summarized by study arm in the clinical study report and/or manuscript (e.g., in the CONSORT flow diagram or descriptive tables).

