	
-Only LDCT (image and standardized report) will be available to the clinician (first intervention arm). CXR and LUS will be performed but not available (clinician will be blinded to CXR and LUS)
 
-Only LUS (image and standardized report) will be available to the clinician (second intervention arm). CXR and LDCT will be performed but not available (clinician will be blinded to CXR and LDCT)
 
The blinding will be maintained during the first 5 days, and hence will not influence the diagnosis and the treatment of the patient. Before discharge of the ED, the clinician in charge will be asked to assess on a 3-level Likert scale the probability of pneumonia (high, intermediate, low level) while considering all available clinical and biological data, plus the imaging modality according to the randomization arm.
 
He will document the intended treatment strategy (antibiotic prescription or not, which molecule, for which indication if not for pneumonia, intended duration).
 
He will be allowed to prescribe antibiotic for another indication than pneumonia by documenting a principal alternative diagnosis (e.g. urinary tract infection, acute exacerbation of a chronic obstructive pulmonary disease, cardiac failure...) and strongly encouraged not to prescribe antibiotic for pneumonia if he rated a low probability of the disease.
 
Patients will be followed-up daily during the hospitalization by research staff and by phone up to 3 months to assess readmission as well as mortality.
 
A previously trained panel of experts will adjudicate the final diagnosis in all patients, having access to all data (clinical, CXR, LDCT and LUS and outcome data at day 28), while blinded to the allocation arm. Their diagnosis will be considered as the reference diagnosis.
 
Safety
 
Number of death and admissions to the ICU in each arm will be communicated to a dedicated data safety monitoring board after 200 inclusions for a safety interim analysis.
 
Blinding of the imaging modalities: For each patient, the two blinded imaging modalities will be registered on a secured research picture archiving and communication system (PACS). The CRFs filled for these imaging modalities will be kept unavailable during the time of the blinding.
 
Unblinding: The research staff will ensure that unblinding (of imaging and CRF) is done at day 5 and that all results are available in the electronic health record.
 
Unblinding will be performed at the ED if the radiologist/clinician performing LUS diagnoses immediately life-threatening findings: pneumothorax, pleural effusion in large quantities (white lung) with mediastinal shift, complete atelectasis of one lung, indirect sign of aneurysmal rupture (haemomediastinum), massive pericardial effusion, tracheal foreign body, pneumoperitoneum, haemothorax, pneumomediastinum, suspicion of acute tuberculosis.
 
Pulmonary embolism won't be excluded as LDCT will be performed without intravenous contrast.

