4.3 Study procedures

3 years (2 years of recruitment plus 3 months of follow-up for OCTOPLUS and one year for GEROBIOTA), inclusions on working days and hours (see Figure 1)

CXR will be interpreted in real-time by a first radiologist and a CRF will be filled in, including the probability of pneumonia.

LDCT will be interpreted in real-time by another radiologist and a CRF will be filled in, including the probability of pneumonia. Both will be blinded to the other's interpretation.

LUS will be performed by another clinician than the one in charge of the patient, and his practice of LUS will be standardized before the launching of the study.

After identification in the ED, included patients will be randomized 1:1:1 to one of the following three arms (stratified by participating center):

-Only CXR (image and CRF) will be available to the clinician (control arm). LDCT and LUS will be performed but not available (clinician will be blinded to LDCT and LUS)

-Only LDCT (image and CRF) will be available to the clinician (first intervention arm). CXR and

LUS will be performed but not available (clinician will be blinded to CXR and LUS)

-Only LUS (image and CRF) will be available to the clinician (second intervention arm). CXR and LDCT will be performed but not available (clinician will be blinded to CXR and LDCT)

The blinding will be maintained during the first 5 days, and hence will not influence the diagnosis and the treatment of the patient.

Before discharge of the ED, the clinician in charge will be asked to assess on a 3-level Likert scale the probability of pneumonia (high, intermediate, low level) while considering all available clinical and biological data, plus the imaging modality according to the randomization arm.

He will document the intended treatment strategy (antibiotic prescription or not, which molecule, for which indication if not for pneumonia, intended duration).

He will be allowed to prescribe antibiotic for another indication than pneumonia by documenting a principal alternative diagnosis (e.g. urinary tract infection, acute exacerbation of a chronic obstructive pulmonary disease, cardiac failure...) and strongly encouraged not to prescribe antibiotic for pneumonia if he rated a low probability of the disease.

Patients will be followed-up daily during the hospitalization by research staff and by phone up to 3 months to assess readmission as well as mortality.

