#### **Physician in charge**

The treating physician was aware of the allocation group. However, he was blinded to the results of the two non-assigned radiological examinations, which were concealed for 5 days. The examinations to be masked were known to the research staff immediately after randomisation. Emergency unblinding was permitted in the occurrence of an immediately life-threatening finding (see Box 2).

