### 8.1.2.2 Diagnostic outcomes

The outcomes to be analysed may consist of either

- (1) the response provided by the **physician in charge**, or
- (2) the response from the **study expert investigator** following the first round of the

**Delphi survey.** At that stage, the expert only has access to REDCap data — i.e., the examination results — but not the imaging series or the full patient record.

- **Unmasked imaging modalities in emergency.** Urgent need to unblind the examination in case of immediately life-threatening findings (yes/no) was collected for each exam (CXR / LDCT / LUS). See [Box2](#).
- **Alternative/concomitant diagnoses** provided by (2) the **study expert** following the 1st round of the Delphi survey. Experts were asked about:
  - **alternative** diagnosis in case of a *low* probability of pneumonia
  - **concomitant** diagnosis in case of an *intermediate* or *higher* probability of pneumonia.the experts could choose among
  - Cardiac Failure
  - Exacerbation COPD/emphysema/asthma
  - Acute bronchitis
  - Pulmonary malignancy
  - Interstitial lung disease
  - Pneumothorax
  - Other
- **Probability of aspiration pneumonia** provided by (2) the **study expert**. Experts were asked to rate the probability as low/intermediate/high in case of a *low* probability of pneumonia
- **Type of pneumonia** according to (2) the **study expert** (viral or bacterial). Experts were asked to provide the type of pneumonia in case of a *low* probability of pneumonia.
- **Additional imaging studies ordered during the acute setting** by (1) the **physician in charge**  
The following additional imaging performed by the physician in charge were collected. For each type of imaging, its number was also collected
  - Chest X Ray
  - Pulmonary CT scanner
  - Lung ultrasound by radiologist
  - Echocardiography by a cardiologist
- **Other procedures prescribed during the acute setting** by (1) the **physician in charge**
  - Non-invasive ventilation
  - Pleural puncture (“*thoracentesis*”, indicated in the one month visit *instrument*)

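### The per-protocol rule makes no exception for permitted emergency unmasking, so the LDCT and CXR arms can lose different kinds of patients from the per-protocol comparison

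*SAP*

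**What the plan says.** SAP section 5 predefines one major deviation: "The blinding of the radiological examinations to be masked from the treating physicians was broken before or during the clinician assessment". The assessment meant is the clinician's pneumonia rating, and no exception is stated. SAP 4.2.2 restricts the per-protocol set to "patients who actually received the exam to which they were randomly assigned and who have no major protocol violations", and SAP 8.2.2.6 repeats the primary analysis on that set.

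The same documents provide for unmasking in an emergency. SAP 3.8 says: "Emergency unblinding was permitted in the occurrence of an immediately life-threatening finding". The protocol synopsis (Study procedures) says: "Unblinding will be performed at the ED if the radiologist/clinician performing LUS diagnoses immediately life-threatening findings". Protocol 4.3 gives the same procedure and sets the time of the primary-outcome rating: "Before discharge of the ED, the clinician in charge will be asked to assess on a 3-level Likert scale the probability of pneumonia".

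Protocol 4.3 also fixes what is masked. LDCT and LUS are masked in the CXR arm, CXR and LUS in the LDCT arm, and CXR and LDCT in the LUS arm.

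On data, SAP 8.1.2.2 says: "Urgent need to unblind the examination in case of immediately life-threatening findings (yes/no) was collected for each exam (CXR / LDCT / LUS". SAP 8.2.3.2 then plans one overall description of these unmaskings, not one by arm.

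Protocol 5.1 names non-receipt and crossover as the per-protocol exclusions, and protocol 4.4 adds protocol violations in general. SAP section 9 does not list the masking rule among its changes.

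**The concern.** Whether a patient leaves the per-protocol set depends on an event after randomisation, and what triggers that event depends on the arm. Take an emergency that only LDCT shows. In the CXR or LUS arm the clinician is shown a masked exam, the rule is met, and the patient is excluded. In the LDCT arm the clinician already has that exam, no masking is broken, and a patient with the same finding stays.

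The per-protocol repeat is there to test whether the primary result is robust. If its arms have been filtered by different findings, a gap between it and the primary result could come from the filter and not from adherence.

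The text can also be read two ways. Section 5 speaks of deviations and 4.2.2 of violations, and a procedure that the protocol permits is arguably neither. Two analysts could build different per-protocol sets from the same SAP.

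**Working it through.** **1. The plan's own figure.** SAP 3.5 gives 68% accuracy with CXR, 84% with LDCT, two-sided alpha 0.05, 90% power and 150 per arm. With the pooled-variance formula and mean accuracy 0.76:

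n = [1.960 × √(2 × 0.76 × 0.24) + 1.282 × √(0.68 × 0.32 + 0.84 × 0.16)]² / 0.16² = (1.184 + 0.760)² / 0.0256 ≈ 148.

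This agrees with 150, which gives 90.4% power. The target of 165 per arm is 150 × 1.10. The point does not depend on these figures; they set the scale.

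**2. Who is excluded, by finding and arm.** This assumes that unmasking comes before or during the rating.

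| Emergency seen on | CXR arm | LDCT arm | LUS arm |
|---|---|---|---|
| LDCT only | excluded | kept | excluded |
| CXR only | kept | excluded | excluded |
| LUS only | excluded | excluded | kept |
| LDCT and CXR, both unmasked where masked | excluded | excluded | excluded |

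For LDCT against CXR, the first two rows create the difference, and they work in opposite directions.

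**3. Size if LDCT-only emergencies dominate.** Let e be the share of patients with an LDCT-only emergency unmasked before the rating, a_e the accuracy in those patients and a_o the accuracy in all others. Suppose there is no true arm effect.

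- LDCT arm, per protocol: (1 − e) × a_o + e × a_e
- CXR arm, per protocol: a_o
- Spurious difference, LDCT − CXR: e × (a_e − a_o)

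The documents give neither e nor a_e. I assume e of 1%, 2% or 5%, and a_e − a_o between −0.5 and +0.2. Around a mean accuracy of 0.76 that puts a_e between 0.26 and 0.96.

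| e (assumed) | Removed of 165, CXR arm | Removed of 165, LDCT arm | Spurious difference (points) |
|---|---|---|---|
| 1% | 1.7 | 0 | −0.5 to +0.2 |
| 2% | 3.3 | 0 | −1.0 to +0.4 |
| 5% | 8.2 | 0 | −2.5 to +1.0 |

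**4. Overlap between modalities.** At 2%, if half of the LDCT-detected emergencies are also unmasked from a masked CXR or LUS, the LDCT arm loses 165 × 0.02 × 0.5 = 1.65 patients against 3.3 in the CXR arm. With 80% overlap it loses 2.64. The imbalance in numbers shrinks accordingly.

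**5. Extremes for the CXR arm alone.** Start from 112/165 = 67.9% and remove 3, 5 or 8 patients (assumed).

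- All removed patients rated correctly: 109/162 = 67.3%, 107/160 = 66.9%, 104/157 = 66.2%.
- All rated wrongly: 112/162 = 69.1%, 112/160 = 70.0%, 112/157 = 71.3%.

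CXR-arm accuracy therefore moves by −1.6 to +3.5 points, so the sign is open.

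**The case against.** There is a good reason for the rule. A CXR-arm clinician who saw the LDCT before rating did not follow a CXR-only strategy. Removing that rating takes out contamination, and section 5 is aimed at events that compromise evaluation of the primary outcome. Part of any shift is therefore intended. This stands, and it is why simply keeping all permitted unmaskings in the set is not a clean answer.

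The rule is also reciprocal, since CXR-only emergencies leave the LDCT arm. A net imbalance in numbers needs one modality to flag more emergencies than the other, and no rates are given. This stands too, although with equal numbers the arms would still lose different kinds of patients.

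A reader might infer that the same patients always stay in the LDCT arm. That holds only for findings that LDCT alone shows. If a masked CXR or LUS shows the finding as well and is unmasked, the LDCT-arm patient leaves too.

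A reader might also infer that the rule favours LDCT, because clinicians shown the LDCT were probably right. The documents do not support a direction, and the ranges above cover both signs.

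Finally, section 5 promises deviations by arm, so the exclusions will be visible. It does not promise to separate permitted unmasking from a breach.

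**Conclusion.** The wording problem is real and limited. As written, section 5 counts permitted emergency unmasking before or during the rating as a major deviation, and 4.2.2 turns that into exclusions that depend on which exam was masked. The per-protocol comparison of LDCT with CXR is then not like for like.

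Under the assumptions in the working (1% to 5% of patients, accuracy differing by −0.5 to +0.2, no offset from CXR-only emergencies), the distortion is about −2.5 to +1.0 points. The planned difference is 16 points. Its standard error at 165 per arm is about √(0.352/165) = 4.6 points, where 0.352 = 0.68 × 0.32 + 0.84 × 0.16. The effect is probably small and its direction is unknown.

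A reader might take this as a threat to the trial's main result. It is not: under SAP 8.2 the primary analysis uses the full analysis set, which this rule does not touch. Unmasking after the rating does not count either.

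One related matter affects the remedy. The emergency list in protocol 4.3 and the synopsis includes large pleural effusion with mediastinal shift and complete atelectasis of one lung. SAP Box 2 omits both and adds indirect signs of aortic dissection and malignant airway obstruction. The list decides which unmaskings were permitted, so the two must be reconciled.

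**What to change.** Before database lock:

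1. In SAP 5 and 4.2.2, separate permitted emergency unmasking from every other break of masking, and keep only the latter as a major deviation. Use one term in both sections.
2. For the per-protocol comparison, exclude from all three arms alike any patient with the urgent-unblinding flag on any of the three exams. All three exams were planned for every patient, so this removes contaminated ratings and keeps the arms comparable.
3. First confirm that the flag was completed for the allocated exam as well as the masked ones. SAP 8.1.2.2 says that it was collected for each exam, but not that this held whatever the arm, and an allocated exam has nothing to unblind.
4. If the flag was completed only for masked exams, run the per-protocol analysis with and without the permitted emergency unmaskings, and report their number by arm.
5. Reconcile the emergency lists in the protocol and SAP Box 2, and state which list governed the unmaskings that took place.

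The cost is SAP wording and a check of one data field. The symmetric exclusion also removes a few fully compliant patients, from a sensitivity set only.

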## 6. Study population

### 6.1 Screening data, eligibility

#### **Patient eligibility criteria**

To be eligible for study participation, all patients will be required to meet the following inclusion criteria, and none of the exclusion criteria:

#### **Inclusion criteria**

[figure not shown]
1. Suspicion of community acquired pneumonia (CAP) or nursing-home acquired pneumonia consulting to the ED
2. Age>65 years
3. Signed informed consent
4. Presence of at least one respiratory symptom (new or increasing cough or dyspnoea, purulent sputum, pleuritic chest pain, respiratory rate >20/min, focal auscultatory findings or oxygen saturation <90% on room air)
5. At least one sign or laboratory finding compatible with an infection will be required
  - temperature >37.8°C or <36.0°C
  - CRP >10 mg/L
  - PCT >0.25µg/L
  - leukocyte count >10G/L with >85% neutrophils or with band forms

Presence of acute delirium or unexplained acute fall can substitute for the presence of either the respiratory or the infectious symptom in patients older than 80 years

#### **Exclusion criteria:**

1. Need for an immediate admission to the intensive care unit (ICU)
2. Diagnosis of pneumonia in the past 3 months
3. SARS CoV-2 infection diagnosed by PCR or antigenic test within the past 3 weeks
4. Transfer from another hospital with a diagnosis of pneumonia
5. Thoracic CXR or CT scan or US already performed during the present episode
6. Need for an immediate contrast-enhanced CT
7. Advanced care planning limiting therapy to comfort care only
8. Prisoners
9. Known uncontrolled psychiatric disorders
10. Previous enrolment into the current study

## 6.2 CONSORT flow diagram

FAS: full analysis set ; PP: per protocol

## 6.3 Baseline patient characteristics

Patient characteristics measured at baseline consist of:

- Demographic data (Age, gender, place of living etc.)
- Comorbidities
- Vaccination status
- Current medication
- Vital signs
- Clinical status (symptoms, etc.)

- Severity score (CURB65, PSI, etc.)
- Biological data
- Microbiological data
- Radiological data
- Treatment
- Quality of life

Which characteristics will be described and how they will be presented are detailed in chapter [8.2.1 Patients' characteristics \(table1\)](#).

## 7. Data Management

### 7.1 Data export

Data were collected using REDCap. Data will be exported from REDCap using the “R statistical software” export format. Technically, raw data will be exported as CSV files and REDCap will provide R scripts to preprocess the data for analysis in R. All data will be stored on the secure servers of the Geneva University Hospitals (HUG).

### 7.2 Data validation

The data validation was performed in accordance with the central data monitoring plan developed by the UIC.

### 7.3 Data sharing

UAM will not share the data.

## 8. Statistical analysis

### 8.1 Outcome definitions

#### 8.1.1 Definition of primary outcome

The primary outcome is the **accuracy** of the treating physician's diagnosis using the panel of study experts' diagnosis as reference.

- I. The physician in charge assessed the probability of pneumonia using a three-point Likert scale
  1. 'low'
  2. 'intermediate'
  3. 'high'
  
- II. The panel of study experts assessed the probability of pneumonia using a five-point Likert scale
  1. 'excluded' (<10% probability); considered as '**low**' on a three-point Likert scale
  2. 'improbable' (10-33%); considered as '**low**' on a three-point Likert scale
  3. 'possible' (34-66%); considered as '**intermediate**' on a three-point Likert scale
  4. 'likely' (67-90%); considered as '**high**' on a three-point Likert scale
  5. 'confirmed' (>90% probability); considered as '**high**' on a three-point Likert scale

Finally, the diagnosis of pneumonia will be classified as follow

- I. When assessed by the physician in charge:
  - positive (pneumonia) if the probability is rated as 'intermediate' or 'high'
  - negative (pneumonia-free) if the probability is rated 'low'
  
- II. When assessed by the panel of study experts (**reference standard**):
  - positive (**pneumonia**) if the probability is rated 'possible', 'likely' or 'confirmed'
  - negative (**pneumonia-free**) if the probability is rated as 'excluded', or 'improbable'

By defining the following elements:

**Actual positives** are those diagnosed with pneumonia by the **panel of study experts**

**Actual negatives** are cases that experts have diagnosed as pneumonia-free

**True Positives** are actual positives diagnosed with pneumonia by the physician in charge

**False Positives** are actual positives that clinician has diagnosed as pneumonia-free

**False negatives** are actual negatives diagnosed with pneumonia by the physician in charge

**True negatives** are actual negatives that clinician has diagnosed as pneumonia-free

The clinician's diagnosis will be considered **accurate** if it is a true positive or a true negative.

The primary endpoint is **diagnostic accuracy**, the proportion of correct diagnoses made by the treating physicians. **Diagnostic accuracy** will be calculated as:

$$\text{Accuracy} = \frac{\text{True Positives} + \text{True Negatives}}{\text{Total Number of Cases}}$$

**Additional diagnostic performance measures** of the treating physician (sensitivity, specificity, PPV, NPV, PLR, NLR) will be evaluated according to the aforementioned definitions.

